DMD	Duchenne muscular dystrophy
DNHS	Duchenne Natural History Study
DSMB	Data and Safety Monitoring Board
DSUR	Drug Safety Update Reports
ECG	Electrocardiogram
eCRF	Electronic case report form
EU	European Union
FDA	Food and Drug Administration
GC	Glucocorticoid
GCP	Good Clinical Practice
GFR	Glomerular filtration rate
HB	Hepatitis B
HCV	Hepatitis C Virus
HEENT	Head, ears, eyes, nose, and throat
HIPAA	Health Insurance Portability and Accountability Act
HIV	Human Immunodeficiency Virus
IB	Investigator's Brochure
ICF	Informed consent form
ICH	International Council for Harmonisation
IEC	Independent Ethics Committee
IND	Investigational New Drug

Clinical Study Protocol: NS-065/NCNP-01-301

IPIM	Investigational Product Information Manual
IRB	Institutional Review Board
IV	Intravenous(ly)
K	Potassium
kg	Kilogram
LC-MS/MS	Liquid Chromatography Tandem Mass Spectrometry
LLOQ	Lower limit of quantification
MedDRA	Medical Dictionary for Regulatory Activities
mITT	Modified intention to treat
MLPA	Multiplex Ligation-dependent Probe Amplification
MMRM	Mixed effect model repeat measurement
mRNA	Messenger ribonucleic acid
MS	Mass spectrometry
Na	Sodium
NCNP	National Center of Neurology and Psychiatry, Japan
N/D	Not done
NOAEL	No observed adverse effect level
NSAA	North Star Ambulatory Assessment
NSP	NS Pharma, Inc.
NS-065/NCNP-01	NS-065/NCNP-01 drug substance
NS-065/NCNP-01 Injection 250 mg	NS-065/NCNP-01 investigational drug substance solution (250 mg vial strength)
PARS III Questionnaire	Personal Adjustment and Role Skills Scale, 3 rd edition
PCR	Polymerase chain reaction
PHI	Protected Health Information
PK	Pharmacokinetic
PMO	Phosphorodiamidate morpholino oligomer
PODCI	Pediatric Outcome Data Collection Instrument
PT-INR	Prothrombin Time – International Normalized Ratio
QMT	Quantitative Muscle Testing
QWBA	Quantitative whole-body autoradiography
RT-PCR	Reverse transcriptase polymerase chain reaction
RBC	Red blood cell count
Ret	Reticulocyte
RIPA	Radioimmunoprecipitation assay
RNA	Ribonucleic acid
RT-PCR	Reverse transcriptase polymerase chain reaction
SAE	Serious Adverse Event
SAP	Statistical analysis plan
SD	Standard deviation
SRM	Study Reference Manual
SUSAR	Suspected unexpected serious adverse reaction
t _{1/2}	Terminal Elimination Half-Life
T _{max}	Time of Maximum Drug Concentration
TEAEs	Treatment-emergent AEs

NCT04060199

NS-065/NCNP-01

Clinical Study Protocol: NS-065/NCNP-01-301

NS Pharma, Inc.

v4.0 08Dec2022

TICVAD	Totally implantable central venous access device
TK	Toxicokinetic
TNF- α	Tumor necrosis factor-alpha
TTCLIMB	Time to Climb 4 Stairs Test
TTRW	Time to Run/Walk 10 Meters Test
TTSTAND	Time to Stand Test
UPCR	Urine protein to creatinine ratio
US	United States
WBC	White blood cell count

2 INTRODUCTION

2.1 Rationale for Study Design, Control Group, and Dose Selection

2.1.1 Rationale for Dose Selection

The dose (80 mg/kg/week for 48 weeks) for this study was based on the successful treatment of participants at 80 mg/kg/week in Study NS-065/NCNP-01-201 for up to a total of 24 weeks of treatment, as well as in the Phase 1/2 Study NS-065/NCNP-01-P1/2 conducted in Japan (Japan P1/2). Results are detailed below.

Viltolarsen dystrophin levels and exon skipping ratio were assessed in Japan P1/2 (Study NS065/NCNP01-P1/2) and Study NS-065/NCNP-01-201. The results are summarized below:

1. Highest dystrophin production measured by Western Blot at 20 to 24 weeks in both Japan P1/2 (Study NS065/NCNP01-P1/2 [n = 4]) and Study NS-065/NCNP-01-201 (n = 8) studies were observed at 80 mg/kg.
2. Average dystrophin production by group measured by Western Blot at 24 weeks in Japan P1/2 (Study NS065/NCNP01-P1/2) was higher at 80 mg/kg (n = 4).
3. Average dystrophin production [REDACTED] measured by Western Blot at 20 to 24 weeks in both Japan P1/2 (Study NS065/NCNP01-P1/2) and Study NS-065/NCNP-01-201 (n = 3) were higher at 80 mg/kg.

[REDACTED]
[REDACTED]
[REDACTED]

4. Average % of dystrophin positive fiber by group measured by immunofluorescence in Study NS-065/NCNP-01-201 was higher at 80 mg/kg (n = 8).
5. Average exon skipping ratio by group measured by RT-PCR in both Japan P1/2 (NS065/NCNP01-P1/2) and Study NS-065/NCNP-01-201 were higher at 80 mg/kg.
6. Safety profiles were comparable in both Japan P1/2 (NS065/NCNP01-P1/2) and Study NS-065/NCNP-01-201 studies between 40 and 80 mg/kg.

Study NS-065/NCNP-01-201) have enrolled a total of 16 participants. As of 28 February 2018, there have been no apparent drug-related serious adverse events (SAEs) reported, and no adverse events (AEs) led to study drug discontinuation. One SAE (left tibia/fibula fracture required hospitalization for surgery, not-related to drug) was reported in June 2018. Safety profiles were comparable for both studies at 40 mg/kg and 80 mg/kg.

In summary, the dose of 80 mg/kg/week for 48 weeks is supported, based on dystrophin production at 80 mg/kg/week and safety profile (well-tolerated for 168 weeks) in the 2 studies (Japan P1/2 (NS065/NCNP01-P1/2) and Study NS-065/NCNP-01-201) conducted to date.

2.1.2 Rationale for Study Design and Control Group

The sponsor indicated its preference to conduct a single global confirmatory trial and expressed concerns about the impact on enrolling for a placebo-controlled trial after an accelerated approval is granted in the United States (US) and Japan. The Food and Drug Administration (FDA) explained the complexity in interpreting a study with natural history as a control group due to the heterogeneity of the disease progression in Duchenne muscular dystrophy (DMD), unless the drug effect is very large. Therefore, the FDA reiterated their position that a placebo controlled study would be required.

2.1.3 Rationale for the Primary Endpoint and Age Range

The primary endpoint for this study is the Time to Stand Test (TTSTAND). The rationale for using TTSTAND as the primary endpoint is:

- TTSTAND is an objective endpoint that can be measured in a standardized way,
- TTSTAND is well validated,
- TTSTAND is clinically meaningful as a measure of patient function, and
- TTSTAND is an important prognostic factor and more generally can predict disease progression.

TTSTAND is the first functional milestone lost in DMD disease progression ([McDonald et al, 2018](#); [Arora et al, in press](#)). The sponsor intends to use velocity rather than time (seconds)

because the velocity measure is superior to the time (seconds) measure in handling large values as patients begin to lose the ability to stand.

In consideration of boys with DMD who could perform functional tests ([Arora et al, in press](#)), age range with 4 to <8 years is selected.

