5.2 Design Implementation

5.2.1 Randomization

Participants are randomly assigned to either 80 mg/kg/week viltolarsen or placebo in a 1:1 ratio. Randomization is carried out with dynamic allocation by minimization method with the biased-coin method. The allocation factors are gene mutation and baseline values for TTSTAND, and region (North America, South America, European Union [EU], and Asia). [REDACTED]

[REDACTED]

The randomization schedule will be generated by an unblinded statistician and maintained by the contract manufacturing organization (CMO). All other parties will be blinded to the randomization.

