12.2 Determination of Sample Size

For TTSTAND (calculated as a velocity, defined as rise per second), the sample size of 74 participants has been calculated using the following values:

- Mean difference = 0.05
- Standard deviation = 0.075
- Type I error level (two-sided) = 0.05
- Power level = 0.8
- Allocation ratio (N1: viltolarsen/N2: placebo) = 1

The mean difference and the SD were set based on the result of comparison between viltolarsen group and natural history control group at 25 weeks in the Phase 2 Study NS-065/NCNP-01-201 (mean difference between 2 groups: 0.0395, SD: 0.07545 and 0.07377). As the mean difference between the 2 groups at 48 weeks is expected to be larger than at 25 weeks, the mean difference was estimated to be 0.05.

An unpaired t-test for analysis was used instead of mixed effect model repeat measurement (MMRM) for the calculation method due to lack of prior information.

When approximately 90% of participants are enrolled in the study, an unblinded review will be conducted and sample size re-estimation will be considered. An additional unblinded review and re-estimation will be performed when approximately 50 participants have completed the Week 49 evaluations for the primary outcome measure. See [Section 12.8](#) for details.

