12.5 Efficacy Endpoints

All efficacy analyses will be performed using the modified intent to treat (mITT) population. In addition, additional analyses will utilize the placebo treatment group.

A hierarchical analysis, following a fixed-sequence hypothesis testing method, is used to first test TTSTAND and then TTRW, 6MWT, NSAA, TTCLIMB, and hand-held dynamometer, if the former was statistically significant.

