12.5.2.2 Analysis Comparing Viltolarsen to Placebo

TTSTAND, TTRW, 6MWT, NSAA, TTCLIMB, and hand-held dynamometer results will be compared between the viltolarsen treated participants and the placebo treated participants using MMRM analysis with treatment group, week of the visit, and the treatment-by-week interaction as factors, and age as one covariate, and baseline performance as a second covariate. The TTRW and TTCLIMB times to perform the test will be converted to velocities. For a test that the participant could not perform, the velocity will be set to zero.

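### The secondary-endpoint models appear to omit baseline TTSTAND, an allocation factor that the protocol calls prognostic, so the fixed-sequence secondary tests may lose some precision

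*Combined protocol and SAP*

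**What the plan says.** Section 2.1.3, arguing for the primary endpoint, says that "TTSTAND is an important prognostic factor and more generally can predict disease progression". Section 5.2.1 then uses it in the design: "Randomization is carried out with dynamic allocation by minimization method with the biased-coin method", and "The allocation factors are gene mutation and baseline values for TTSTAND, and region".

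Section 12.5.2.2 describes a single analysis for six tests: "TTSTAND, TTRW, 6MWT, NSAA, TTCLIMB, and hand-held dynamometer results will be compared between the viltolarsen treated participants and the placebo treated participants using MMRM analysis". The factors are treatment, week and their interaction, with "age as one covariate, and baseline performance as a second covariate". It does not say which test's baseline is meant.

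Section 12.5 sets a fixed sequence that "is used to first test TTSTAND and then TTRW, 6MWT, NSAA, TTCLIMB, and hand-held dynamometer, if the former was statistically significant". Section 12.1 says that a SAP will give further detail and will take precedence over the protocol. The document reviewed contains no separate SAP text.

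**The concern.** In the primary model, baseline performance is baseline TTSTAND, so the allocation factor is adjusted for. In the secondary models the natural reading is own-test baseline: baseline TTRW for TTRW, baseline 6MWT for 6MWT, and so on. Baseline TTSTAND then drops out of all five, although inclusion criterion 5 requires the test before dosing in every boy.

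Two consequences follow if baseline TTSTAND still predicts the Week 49 result after age and own-test baseline.

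- Variation that the model could have explained stays in the residual, so the standard error is larger than it need be.
- Minimisation has already balanced this factor between the arms. The true sampling variance of the treatment effect is therefore lower than a model without the factor reports, and the test rejects somewhat less often than its nominal level.

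The fixed sequence raises the stakes, because a miss at TTRW stops formal testing of the other four.

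**Working it through.** **Step 1. Reproduce the plan's own figure.** In Section 12.2, "the sample size of 74 participants has been calculated using the following values": difference 0.05, SD 0.075, two-sided alpha 0.05, power 0.8, 1:1 allocation, unpaired t-test. With 37 per arm, the noncentrality is 0.05 / (0.075 × √(2/37)) = 2.87 on 72 degrees of freedom, and power is 0.808. With 36 per arm it is 0.797. So 37 per arm, 74 in total, is reproduced. The figure concerns the primary endpoint only. No SD, effect or power is given for any secondary endpoint.

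**Step 2. Inputs for the secondary models.** N = 74 comes from Section 12.2. The partial correlation r between baseline TTSTAND and a Week 49 secondary result, given age and own-test baseline, is not in the documents. It is assumed here over 0 to 0.4. Also assumed are 80% power for the planned model, a single-visit ANCOVA in place of the MMRM, and no dropout.

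**Step 3. Formulas.**
- Standard error relative to the planned model: √(1 − r²).
- Equivalent sample size: 74 / (1 − r²).
- Power: noncentral t at 37 per arm. The planned model (intercept, treatment, age, own baseline) has 74 − 4 = 70 degrees of freedom, and the adjusted model has 69. A difference of 0.660 residual SDs gives the planned model 80%. With the added covariate the noncentrality becomes 0.660 / (√(1 − r²) × √(2/37)).

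| Assumed r | Relative SE | SE reduction | Power | Equivalent N |
|---|---|---|---|---|
| 0 | 1.000 | 0% | 80.0% | 74.0 |
| 0.2 | √0.96 = 0.980 | 2.0% | 81.6% | 77.1 |
| 0.3 | √0.91 = 0.954 | 4.6% | 83.6% | 81.3 |
| 0.4 | √0.84 = 0.917 | 8.3% | 86.3% | 88.1 |

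At the final-stage alpha of 0.049 (Section 12.8) the results agree to within 0.1 percentage point.

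**Step 4. Cost if the covariate is weak.** Under simple randomisation, chance imbalance in an added covariate multiplies the variance by about 1 + 1/69. The net gain is then nil or negative when |r| is below √(1 − 1/(1 + 1/69)) = 0.12. At r = 0, power would fall from 80.0% to 79.4%. Balancing on TTSTAND reduces this cost.

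**Step 5. Simulation check.** This used 3,000 trials per setting with 74 boys. Assumptions: a biased coin of 0.8 on a median split of baseline TTSTAND, a correlation of 0.6 between baseline TTSTAND and own-test baseline, a true effect of 0.66 residual SDs, and no separate age term.

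| Assumed r | Power, omitted → included | Null rejection at 5%, omitted → included |
|---|---|---|
| 0 | 80.0% → 80.0% | 4.4% → 4.8% |
| 0.2 | 80.4% → 81.8% | 4.7% → 5.0% |
| 0.4 | 79.7% → 84.5% | 3.3% → 4.5% |

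Monte Carlo error is about √(0.8 × 0.2 / 3000) = 0.7 point for power and √(0.05 × 0.95 / 3000) = 0.4 point for null rejection. The power gains of 1.4 and 4.8 points are a little below the 1.6 and 6.3 points of Step 3.

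A second simulation used 2,500 trials per setting, minimisation on three factors and a correlation of 0.7. For 4%, 9% and 16% of residual variance explained, it gave:
- mean SE from 0.240 to 0.235, 0.247 to 0.237 and 0.255 to 0.236, which are cuts of 2.1%, 4.0% and 7.5%;
- power from 80% to 81%, 81% to 84% and 78% to 85%;
- null rejection with the covariate omitted of about 5.0%, 4.1% and 4.0%.

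**The case against.** A reader might infer that every secondary test in the sequence gives up precision. The documents do not support that. Section 2.1.3 makes a general prognostic claim in support of the primary endpoint. It says nothing about what baseline TTSTAND adds once age and own-test baseline are in the model. For some tests it may add little. The NSAA already scores getting up from the floor (Section 9.15.1.4). Two of the four dynamometer measures are of the elbow (Section 9.15.1.6), and Section 2.2.1 places upper-limb decline after loss of ambulation, whereas these boys are ambulant.

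A reader might also infer bias or an inflated error rate. Neither follows: omitting a balanced factor leaves the comparison unbiased and, if anything, conservative. Age plus own-test baseline is a conventional prespecified adjustment, so this is a missed improvement and not an error.

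Three further objections are fair.

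- The correlations, the coin probability and the cut-point for TTSTAND are assumed. Text after the allocation factors in Section 5.2.1 is redacted.
- Own-test baseline is a reading of an undefined phrase, and the SAP may settle it. If the phrase meant TTSTAND throughout, own-test baseline would be missing instead, so clarification is needed either way.
- Gene mutation and region are also allocation factors that no efficacy model names. That is true, but the protocol calls only TTSTAND prognostic, and this point is confined to it.

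What stands is that the size is unknown and could be nil for particular tests. The omission itself, on the natural reading, also stands.

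**Conclusion.** The point holds as a possible loss of efficiency and a gap in specification. On the natural reading of Section 12.5.2.2, baseline TTSTAND is absent from all five secondary models, although the protocol calls it prognostic and allocates on it. For assumed partial correlations of 0 to 0.4, including it would cut the standard error by 0% to about 8% and raise power from 80% to between 80% and about 86%. The upper figure is nearer 85% in simulation. The conservatism shows clearly only at the top of that range, with null rejection of 3.3% to 4.0% in the two simulations.

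These figures rest on the assumptions in the working. The sample size of 74 and the primary model's adjustment for TTSTAND are unaffected. If the SAP already names this covariate for the secondary endpoints, the point is closed.

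**What to change.** In Section 12.5.2.2 and the SAP, state for TTRW, 6MWT, NSAA, TTCLIMB and each dynamometer measure that the covariates are age, the baseline value of the endpoint being analysed, and baseline TTSTAND velocity. Use the same baseline TTSTAND value as in the primary model, and leave that model's TTSTAND adjustment as it is. If baseline TTSTAND is to stay out of the secondary models, say so and give the reason.

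The cost is one sentence and one model degree of freedom, with no new data. The change must be fixed before database lock, when Section 12.1 has the SAP finalised, and preferably before anyone involved in the analysis sees unblinded results.

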2.1.4 Rationale for Study Duration of 48 Weeks

Individual participant study duration is 48 weeks, which takes into consideration the feasibility of patient enrollment and retention in the proposed placebo-controlled study.

2.2 Disease and Treatment

2.2.1 Duchenne Muscular Dystrophy– Epidemiology and Genetic/Biochemical Basis

DMD is a disorder of progressive weakness leading to severe disability and ultimately death caused by a deficiency of the dystrophin protein. The reported prevalence of DMD is 15.9 cases per 100,000 live male births in the US and 19.5 cases per 100,000 live male births in the UK ([Ryder et al, 2017](#); [Mendell et al, 2012](#); [Moat et al, 2013](#)). The symptoms of DMD are often first noted at about 3 to 5 years of age, although clinical manifestations may be present as early as the first year of life. Proximal leg weakness impairs mobility and precludes the ability to run or to rise from a squatting position. Complete loss of ambulation follows, with a progressive decline of upper extremity strength and function. Declines in respiratory and cardiac function contribute to morbidity later in the disease, ultimately culminating in early lethality ([Bushby et al \[Part 1\], 2018](#); [Birnkrant et al, 2018](#).) The impact of this debilitating condition on those affected by it and their families is significant.

The biochemical basis of DMD is the absence of a functional dystrophin protein in striated muscle tissue that is essential for healthy muscle function and muscle fiber integrity. In normal striated muscle the cytoplasmic dystrophin protein links intracellular actin with the extracellular matrix to provide structural stability of the muscle cell membrane. In the majority of patients with DMD, dystrophin protein is not produced because of out-of-frame mutations characterized by a deletion of one or more exons from the dystrophin gene, which is located on the short arm of the X chromosome. Dystrophin mutations in which some dystrophin protein function remains are associated with a similar, but often milder phenotype, classified as Becker muscular dystrophy (BMD). DMD and BMD exhibit X-linked recessive inheritance.

2.2.2 Current Natural History, Disease Management, and Treatment Recommendations

The Cooperative International Neuromuscular Research Group (CINRG) conducted the largest prospective multi-center natural history study to date in DMD, the CINRG Duchenne Natural History Study (DNHS) (McDonald et al, 2013; Henricson et al, 2013; McDonald et al, 2018). The study includes >400 boys and men with DMD, with variable amounts of longitudinal follow-up over the course of a decade (2006 to 2016). The study has annual follow-up visits that include timed function tests, muscle strength, questionnaire functional assessments, pulmonary function tests, and quality of life assessments.

Since there is currently no cure for DMD, the goal of care is to provide the best quality of life through all stages of the disease. To date, treatments focus on optimizing strength and function through the use of pharmacological interventions, physical therapy, and assistive and adaptive devices.

2.2.3 Glucocorticoid Treatment

At present, treatment with glucocorticoid (GC) medication is the only pharmacological intervention that has been shown to slow the decline of strength and function in DMD patients. The two main GCs used in DMD are prednisone and deflazacort (EMFLAZA™). Daily oral administration of prednisone or deflazacort stabilizes or improves strength and prolongs ambulation (Drachman et al, 1974; Brooke et al, 1987; Griggs et al, 1993; Mendell et al, 1989; Griggs et al, 1991; Fenichel et al, 1991). The mechanism by which GCs are beneficial in dystrophin deficiency is likely multifactorial, including anti-inflammatory actions. The immunosuppressive effects of GCs may not be beneficial, and other immunosuppressants have not shown benefit (Griggs et al, 1993). On February 9, 2017, the US FDA approved EMFLAZA™ for the treatment of patients 5 years of age and older with DMD.

In 2005, the American Academy of Neurology issued a practice parameter regarding GC treatment in DMD and recommended that GC should be offered as treatment, despite known side effects (Moxley et al, 2005). The significant side effects of GCs include Cushingoid features, adverse behavioral changes, obesity, growth retardation, increased risk for bone fractures, gastritis, delayed puberty, cataracts, hypertension, glucose intolerance, susceptibility to infection, and masking of response to stress (Matthews et al, 2016).

2.2.4 Dystrophin Restoring Interventions

New therapies based on specific genotypes are in development. Small molecules that can read through nonsense mutations could potentially treat approximately 13% of DMD patients (Bushby et al, 2014). Exon skipping, which uses antisense oligonucleotides to alter the splicing pattern of the genes is designed to bring out-of-frame deletions into frame. The technology of exon skipping utilizes antisense oligonucleotides that bind to a specific sequence in the messenger ribonucleic acid (mRNA) to alter splicing of exons. By this means, specific exons can be excluded from the final transcript that is exported to the cytoplasm from the nucleus; hence the term ‘exon skipping’. By the design of the oligonucleotide, the out-of-frame deletion can be enlarged to include the adjacent exon such that the resulting deletion is in-frame (Kole and Krieg, 2015).

This new type of treatment could potentially treat 80% of DMD patients who have large-scale deletion or duplication mutations in the dystrophin gene (Aartsma et al, 2009). The full characterization of DMD patient mutations and further development of the technology will be crucial to fully realize these novel therapies as they are developed.

To date, 2 oligonucleotide chemistries have been brought to the stage of human clinical trial: 2’O-methyl phosphorothioate (2’O-Me) antisense oligonucleotides (Voit et al, 2014) and phosphorodiamidate morpholino oligomers (PMO) for skipping of exon 51 in the dystrophin gene (Mendell et al, 2013; Cirak et al, 2012; Cirak et al, 2011).

A 48-week study of the 2’O-Me compound drisapersen did not reach significance in the Six-minute Walk Test (6MWT), which was its primary outcome measure for this Phase 2 study (Voit et al, 2014). The PMO compound eteplirsen was tested in a 48-week study, with the number of muscle fibers showing restored dystrophin as its primary outcome measure (Mendell et al, 2013). Eteplirsen (Exondys 51[®]) was approved by the FDA under the accelerated approval pathway on September 19, 2016.

